3.8.2 Clinical Laboratory Evaluation

The summary statistics (including number, mean, standard deviation, median, minimum and maximum) of all laboratory variables and changes from baseline will

be calculated for each visit or study assessment by treatment group. For parameters of white blood cell counts, neutrophils (absolute count), lymphocytes (absolute count), monocytes (absolute count), hemoglobin, platelets, ALP, ALT, aspartate aminotransaminase, total bilirubin, plots of mean/mean changes from baseline with the corresponding standard error will be displayed.

For shift tables, laboratory results will be classified using the CTCAE Version 5.0. All graded laboratory parameters will be summarized separately for hematology and biochemistry. Corresponding shift tables comparing baseline to the worst post-baseline grade within the treatment period will be provided.

3.8.3 Vital Signs

Descriptive statistics for vital signs (weight, temperature, blood pressure, pulse rate, and respiratory rate) values and the change from baseline will be presented for each scheduled assessment time point.

3.8.4 ECG

Descriptive statistics for ECG parameters (i.e., PR interval, QRS interval, and QTcF interval) at each time point with triplicate ECGs will be presented for the values and change from baseline scores. (QTcF is the QT interval using Fridericia's correction which is calculated by $QTcF = QT/RR^{1/3}$.)

The number and percentage of subjects with observed QTcF values that satisfy the following conditions will be presented by treatment group and study visit and categorized as: ≤ 450 ms; > 450 to 480 ms; > 480 to 500 ms; and > 500 ms.

The number and percentage of subjects having change from baseline QTcF values that satisfy the following conditions will be presented by treatment group and study visit and categorized as: ≤ 0 ms; > 0 to ≤ 30 ms; > 30 to ≤ 60 ms; and > 60 ms.

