5.2.2.2.3 Initial Data from ADPKD Protocol KD019-101

Sixty-one subjects were enrolled into 5 dosing cohorts in the Phase 1b and Phase 2a portions of the study: 9 subjects into Cohort 1 at 50 mg daily, 8 subjects into Cohort 2 at 100 mg daily, 5 subjects into Cohort 3 at 150 mg daily, 14 subjects into Cohort 4 at 150 mg Monday, Wednesday, and Friday, 10 subjects into Cohort 5 at 150 mg Monday and Thursday, and an additional 15 Phase 2a subjects at 50 mg daily (Table 5-1).

Table 5-1: Summary of KD019-101 Dose / Schedule, Demographics and Median TKV (mL)

	Gender (Male [M]/Female [F])	Median Age (Years)	Median TKV (mL)	
24	9M / 15F	39	1401*	
8	5M / 3 F	37	1525	
5	2M / 3 F	41	1094	
14	4M / 10 F	36	1344	
10	4M / 6 F	37	795	
61	24M / 37F	38 (19-55)	1333.5* (411-4432)	
	8 5 14 10	8 5M/3 F 5 2M/3 F 14 4M/10 F 10 4M/6 F	8 5M/3F 37 5 2M/3F 41 14 4M/10F 36 10 4M/6F 37	

Safety reviews after the first 2 cohorts deemed these cohorts to have adequate safety and to be tolerable. In Cohort 3, 3 of 5 subjects enrolled have withdrawn consent primarily due to concerns with rash. It was noted that all 5 subjects in this cohort experienced rash within the first 28 days of treatment. In comparison, 4 out of 9 subjects in the 50-mg cohort and 1 out of 8 subjects in the 100-mg cohort experienced rash within the first 28 days. While rash at the 150 mg dose level did not meet strict safety criteria for defining the MTD, this dose level was considered intolerable for long-term administration in this population. Therefore, the MTD for daily dosing was determined to be 100 mg daily. While the MTD dose of 100 mg/day was based on criteria defined in the protocol, the occurrence of moderate QTc prolongation in 2 subjects dosed at that level led to a decision later in the study to recommend 50 mg/day as the best tolerated daily dose.

As the known toxicities of tesevatinib, including diarrhea and rash, have been seen in all 3 Phase 1b dosing cohorts, an alternative dosing schedule of dosing 150 mg of KD019 on Monday,

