3.8 Safety Analysis

Safety assessments will include AEs, serious adverse events (SAEs), vital sign measurements, clinical laboratory evaluations (hematology and chemistry), and electrocardiograms (ECGs). Unscheduled visits for safety assessments will not be presented in summary tables but will be in listings. All safety analyses will be performed using the safety population for all cohorts and both studies.

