	Table 14.4.15 Summary of Clinical Laboratory: Chemistry
	Table 14.4.16 Summary of Clinical Laboratory: Any Other Clinical Labs
	Table 14.4.17 Shifts from Baseline for Hematology Assessment
	Table 14.4.18 Shifts from Baseline for Chemistry Assessment
	Table 14.4.19 Summary of Vital Sign Results and Change from Baseline
	Table 14.4.20 Summary of 12-Lead ECG and Change from Baseline
	Table 14.4.21 Summary of QTcF Interval Results
	Table 14.4.22 Overall Summary of AEs
	Table 14.4.23 Overall Summary of AEs for Study 101
	[REDACTED]
Listings (16.2.Y.Z)	Listing 16.2.1 Disposition of Subjects
	Listing 16.2.2 Protocol Deviations
	Listing 16.2.3 Patients Excluded From Efficacy Analysis
	Listing 16.2.4 Patient Demographics
	Listing 16.2.5 Dose Changes
	Listing 16.2.6.1 Estimated Glomerular Filtration Rate

	Listing 16.2.6.2 Height Adjusted Total Kidney Volume
	Listing 16.2.7.1 Adverse Events
	Listing 16.2.7.2 Adverse Events leading to Study Drug Discontinuation
	Listing 16.2.7.3 Adverse Events leading to Death
	Listing 16.2.7.4 Serious Adverse Events
	Listing 16.2.8.1 Clinical Laboratory: Hematology
	Listing 16.2.8.2 Clinical Laboratory: Chemistry
	Listing 16.2.8.3 Clinical Laboratory: Any Other Clinical Labs
	Listing 16.2.8.4 Vital Signs
	Listing 16.2.8.5 12-Lead ECG
Efficacy	
Figures (14.3.Y.Z)	Figure 14.3.1 Annualized Change in Estimated Glomerular Filtration Rate
	Figure 14.3.2 Annualized Percent Change from Baseline Height Adjusted Total Kidney Volume

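### QTcF outliers are tabulated by visit only; the SAP should also count each subject once by the worst on-treatment value

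*SAP*

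**What the plan says.** SAP 3.8.4 plans two categorical QTcF summaries.

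- Absolute values: "The number and percentage of subjects with observed QTcF values that satisfy the following conditions will be presented by treatment group and study visit", with the categories "categorized as: ≤ 450 ms; > 450 to 480 ms; > 480 to 500 ms; and > 500 ms".
- Change from baseline: "subjects having change from baseline QTcF values that satisfy the following conditions will be presented by treatment group and study visit", with categories split at 0, 30 and 60 ms.

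The only table titled for QTcF in SAP Section 4 is "Table 14.4.21 Summary of QTcF Interval Results", and its title adds no detail. SAP 3.8 also states: "Unscheduled visits for safety assessments will not be presented in summary tables but will be in listings". For laboratory data, by contrast, SAP 3.8.2 plans a worst-value summary: "Corresponding shift tables comparing baseline to the worst post-baseline grade within the treatment period will be provided".

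On the background, Protocol 5.2.2.2.3 records, for 100 mg daily, that "the occurrence of moderate QTc prolongation in 2 subjects dosed at that level led to a decision later in the study" to recommend 50 mg daily. The protocol's action limits (a rise of more than 60 msec above baseline, or a value of at least 480 msec) apply at any evaluation (Tables 4-1 to 4-4, ECG footnotes).

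**The concern.** A reader of a QT safety summary first wants to know how many subjects in each cohort ever exceeded 450, 480 or 500 ms, or ever rose by more than 60 ms. Rows split by visit do not answer this. Five subjects with one high reading each, at five different visits, give the same rows as one subject who is high at all five.

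The protocol itself reports QT per subject. Section 5.3.1 gives 33 of 169 oncology subjects (20%) with prolongation at some time during treatment, and Table 5-2 counts subjects by size of prolongation. The SAP plans no measured per-subject count of this kind for 50 mg daily, the dose the protocol expects to take forward. Low percentages in every visit row could then be read as a low percentage of subjects affected.

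The visit rows have a second gap. In SILK, ECGs on Days 1 and 14 are taken predose and at 1, 4 and 8 hours (Protocol 9.10), and Protocol 5.3.1 places the QTcF peak at 4 hours on Day 14. The SAP does not say which reading, or whether the highest, represents such a visit in the category tables.

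**Working it through.** The plan states no figure here to reproduce. The check is what the visit rows can and cannot show.

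**1. Bounds.** Let c_v be the number of subjects above a limit at visit v, in a cohort of n. The number ever above it, E, satisfies

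max(c_v) ≤ E ≤ min(n, sum of c_v).

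Both ends can occur: the same subjects at every visit, or different subjects at each.

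**2. Number of ECG visits.**
- Daily dosing outside SILK, to 24 months: Days 1, 7, 14, 21, 28 (5), Months 2 to 12 (11) and Months 14 to 24 every two months (6). Total 5 + 11 + 6 = 22.
- SILK, on treatment to Month 12: the same 5 early days plus Months 3 to 12 (10). Total 15. Month 2 is left out because that ECG is predose after the 28-day drug holiday (Protocol 9.2.4).

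**3. Bounds with one subject above the limit at every visit.**

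| n | Visits | Each row shows | Subjects ever above: lowest | Highest |
|---|---|---|---|---|
| 8 | 5 | 12.5% | 1 (12.5%) | 5 (62.5%) |
| 50 | 15 | 2.0% | 1 (2.0%) | 15 (30.0%) |
| 65 | 22 | 1.5% | 1 (1.5%) | 22 (33.8%) |

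The n = 65 row pools the 15 earlier Phase 2a subjects and the 50 SILK subjects (15 + 50 = 65) and applies the 22-visit schedule to all of them, which is a simplification.

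**4. The 100 mg case.** If both subjects in Protocol 5.2.2.2.3 belonged to the 8-subject 100 mg cohort (an assumption, since others moved to 100 mg later), a per-subject row shows 2/8 = 25%. If they crossed at different visits, no visit row exceeds 1/8 = 12.5%. If they crossed at the same visit, that row shows 25%.

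**5. Dependence on pattern (illustration only).** Suppose 5 of 50 SILK subjects cross a limit (10%, 95% Clopper-Pearson interval 3.3% to 21.8%).
- Each once, at a random one of 15 visits: the average row shows 5/15 = 0.33 subjects, and 0.33/50 = 0.7%.
- All five at Day 14: the Day 14 row shows 5/50 = 10%, the full count.

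The documents do not say which pattern to expect. The dilution therefore runs from none to about one fifteenth, and the lower figure simply reflects the assumed spread over 15 visits.

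**The case against.** The strongest reply is that other planned output covers most of the need.

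- **Adverse event tables.** Under Protocol 9.10, a centrally read rise above 60 msec, or to 480 msec or more, calls for further monitoring. ECG abnormalities that change management, added monitoring included, go on the adverse event form. If sites follow this, confirmed crossings of the action limits reach Tables 14.4.4 and 14.4.4.1, which count adverse events by preferred term and maximum severity. This stands. It leaves uncovered mainly values above 450 and below 480 ms with a rise of 60 ms or less. The tables also show severity grades, which need not match the SAP categories.
- **Listing 16.2.8.5** holds each subject's ECG data, so the count can be derived. This stands too, but a count derived by hand is not a specified analysis.
- **Descriptive statistics** at each timepoint include the maximum (SAP 3.1.3.1 and 3.8.4). That shows whether anyone crossed a limit at that timepoint, not how many subjects did so overall.
- **Clustering.** QTcF rises with concentration and peaks at 4 hours on Day 14, and later scheduled SILK ECGs are predose only. Crossings may well cluster at Day 14, so the diluted figure should not be taken as a forecast.
- **Protocol 14.3.8** says QTc prolongation will be summarised separately, and the title of Table 14.4.21 does not rule out a worst-value block. True, but the SAP text, where the layout is fixed, specifies visit rows only.

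Two stronger readings are tempting. A reader might infer that the trial cannot report the per-subject count at all; the listing and the adverse event tables show otherwise. A reader might also infer that 50 mg daily was chosen on this count. The two cases are described as moderate prolongation, without reference to the SAP's limits, and Protocol 7.2.2 also cites simpler dosing, a severe rash in the Monday/Thursday cohort and the smaller effect of missed doses.

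**Conclusion.** The point holds as a gap in tabulation. The planned summary tables do not give the number of subjects per cohort whose measured QTcF, or change in QTcF, ever crossed a limit on treatment, and the visit rows cannot recover it. The uncertainty can be wide (1.5% to 33.8% in the 65-subject, 22-visit example) or nil if crossings fall at one visit. The bounds need no assumption about pattern; the worked examples do.

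The consequence is modest. Larger prolongations should surface as adverse events if Protocol 9.10 is followed, and no endpoint or decision rule is affected. QTc prolongation in 2 subjects was one of several reasons for moving from 100 mg to 50 mg daily. What is missing is a measured per-subject outlier rate by category, in the form in which the protocol reports earlier QT data. The worst-grade table for laboratory data shows that the SAP already uses this kind of summary elsewhere.

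**What to change.** Add to SAP 3.8.4 and Table 14.4.21 one block per cohort that classifies each subject once by maximum on-treatment QTcF and once by maximum on-treatment change from baseline, over all on-treatment timepoints, in the categories already listed. Keep the by-visit rows as support.

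The text should also settle three details:

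- which reading stands for a visit with several ECG times in the by-visit rows (Days 1 and 14);
- whether unscheduled ECGs count towards the maximum, which would need a stated exception to SAP 3.8;
- how readings around the SILK drug holiday are treated when on-treatment is defined.

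A footnote could mention that the SAP's category above 480 ms excludes a value of exactly 480, which the protocol's action limit includes.

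The cost is one block in an existing table, programmed from data already collected. No ECGs are added and no clinical rule changes.

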3.9 Pharmacokinetic Analysis Plan

PK serum concentration and all biomarkers will be summarized at each collection time-point by cohort for KD019-101.

4 LIST OF TABLES, FIGURES, AND LISTINGS

In all tables, figures and listing, results will be presented by treatment cohorts and overall, unless be otherwise specified.

Table/Listing/Figure	Title
Demographics and Baseline Characteristics	
Tables (14.1.Y.Z)	Table 14.1.1 Screen Failure
	Table 14.1.2 Patient Disposition
	Table 14.1.3 Summary of Demographics and Baseline Characteristics
	Table 14.1.4 Summary of Major Protocol Deviations
	Table 14.1.5 Summary of Medical History
Treatment Exposure and Concomitant Medication	
Tables (14.2.Y.Z)	Table 14.2.1 Summary of Treatment Compliance and Exposure
	Table 14.2.2.a Summary of Prior Medications
	Table 14.2.2.b Summary of Concomitant Medications
Efficacy	
Tables (14.3.Y.Z)	Table 14.3.1 Annualized Change in Estimated Glomerular Filtration Rate
	Table 14.3.2 Annualized Percent Change from Baseline in Height Adjusted Total Kidney Volume
	Table 14.3.3 Annualized Percent Change from Baseline in Reciprocal of Serum Creatinine

	Table 14.3.3.1 Annualized Percent Change from Baseline in Reciprocal of Serum Creatinine for Study 101
Safety	
Tables (14.4.Y.Z)	Table 14.4.1 Summary of AEs
	Table 14.4.1.1 Summary of AEs for Study 101
	[REDACTED]
	Table 14.4.2 Summary of TEAEs
	Table 14.4.2.1 Summary of TEAEs for Study 101
	[REDACTED]
	Table 14.4.3 Summary of TEAEs Related to KD019
	Table 14.4.3.1 Summary of TEAEs Related to KD019 for Study 101
	[REDACTED]
	Table 14.4.4 AEs by Preferred Term and Maximum Severity
	Table 14.4.4.1 AEs by Preferred Term and Maximum Severity for Study 101
	[REDACTED]
	Table 14.4.5 AEs by Preferred Term and Strongest Relationship
	Table 14.4.5.1 AEs by Preferred Term and Strongest Relationship for Study 101
	[REDACTED]
	Table 14.4.6 Summary of Grade ≥ 3 TEAEs by System Organ Class and Preferred Term
	Table 14.4.6.1 Summary of Grade ≥ 3 TEAEs by System Organ Class and Preferred Term for Study 101
	[REDACTED]
	Table 14.4.7 Summary of Grade ≥ 3 TEAEs Related to KD019 by System Organ Class and Preferred Term

	Table 14.4.8 Summary of Serious Adverse Events
	Table 14.4.9 Summary of Serious Adverse Events Related to KD019
	Table 14.4.10 Summary of TEAEs leading to Dose Modification
	Table 14.4.11 Summary of TEAEs Related to KD019 leading to Dose Modification
	Table 14.4.12 Summary of TEAEs leading to Dose Discontinuation
	Table 14.4.13 Summary of TEAEs Related to KD019 leading to Dose Discontinuation
	Table 14.4.14 Summary of Clinical Laboratory: Hematology
	Table 14.4.15 Summary of Clinical Laboratory: Chemistry
	Table 14.4.16 Summary of Clinical Laboratory: Any Other Clinical Labs
	Table 14.4.17 Shifts from Baseline for Hematology Assessment
	Table 14.4.18 Shifts from Baseline for Chemistry Assessment
	Table 14.4.19 Summary of Vital Sign Results and Change from Baseline
	Table 14.4.20 Summary of 12-Lead ECG and Change from Baseline
	Table 14.4.21 Summary of QTcF Interval Results
	Table 14.4.22 Overall Summary of AEs
	Table 14.4.23 Overall Summary of AEs for Study 101
	[REDACTED]
Listings (16.2.Y.Z)	Listing 16.2.1 Disposition of Subjects
	Listing 16.2.2 Protocol Deviations
	Listing 16.2.3 Patients Excluded From Efficacy Analysis
	Listing 16.2.4 Patient Demographics
	Listing 16.2.5 Dose Changes
	Listing 16.2.6.1 Estimated Glomerular Filtration Rate

	Listing 16.2.6.2 Height Adjusted Total Kidney Volume
	Listing 16.2.7.1 Adverse Events
	Listing 16.2.7.2 Adverse Events leading to Study Drug Discontinuation
	Listing 16.2.7.3 Adverse Events leading to Death
	Listing 16.2.7.4 Serious Adverse Events
	Listing 16.2.8.1 Clinical Laboratory: Hematology
	Listing 16.2.8.2 Clinical Laboratory: Chemistry
	Listing 16.2.8.3 Clinical Laboratory: Any Other Clinical Labs
	Listing 16.2.8.4 Vital Signs
	Listing 16.2.8.5 12-Lead ECG
Efficacy	
Figures (14.3.Y.Z)	Figure 14.3.1 Annualized Change in Estimated Glomerular Filtration Rate
	Figure 14.3.2 Annualized Percent Change from Baseline Height Adjusted Total Kidney Volume
